16.2 Financial Support

The study is funded for 2 years from February 2023 by the NIHR Reference NIHR135830.

17.0 Patient and public involvement

The BSI will recruit a Patient and Public Involvement (PPI) panel comprising people with lived experience of different medical conditions that are defined by the participant eligibility criteria of the study. We will ensure the panel comprises diverse ages, ethnicities, a gender balance, represent different disease groups and fair geographical spread. This will be achieved by actively reaching out to patient community groups through supporting charities and networks to ask for expression of interest from people with lived experience. We already have expressions of interest from individuals that meet these criteria from when we set up the pre-grant focus group and are in close liaison with the patient group organisations linked to the conditions we are studying. Individuals who have expressed an interest have lived experience and also PPI experience working with a number of COVID-19 projects. These will include, but is not limited to, people with immunodeficiencies, blood cancer, taking immunosuppressant therapies, chronic organ damage, solid organ transplants and individuals with diabetes.

The PPI panel will meet virtually with the lead investigators right from the start of the project to provide feedback and input into the research protocol and priorities to ensure the voice of people with lived experience is included in all facets of the study. This was discussed in the original focus group and the preference would be to meet virtually as many patients are continuing to practice some form of social distancing and so travel and group meetings are not appealing. The panel will continue to meet regularly with the scientists involved in the study to provide their perspective on the ongoing research and outcomes and how to communicate results to the public.

Sponsor: University of Birmingham

19.0 Dissemination and publication

This urgent research is relevant to the general public and all health care professionals. We will aim to publish as soon as data is available due to urgent clinical and occupational need. Our engagement strategy is three pronged:

Patient engagement: This is a unique population where many are continuing to practice social distancing as highlighted by our grant focus group. We will make it a priority at the first PPI panel meeting to discuss this, particularly with those with lived experience, and how as a community we can best communicate and engage with the immune vulnerable cohorts. In addition, we are working with all the key patient groups and would hope to support or be part of any online or in-person events that they are arranging. Patients will be invited to our in-person stakeholder meetings but will be given the option to attend remotely as well. All the clinicians in this study support patient days and local engagement activities and will use these added value opportunities for STRAVINSKY engagement activities. We will hold in-person local events at the research sites (e.g., a public lecture in Birmingham) if our target audience show enthusiasm for this.

Stakeholder engagement: There will be 2 face-to-face stakeholder meetings that are being arranged by the BSI. These planned and costed events will enable patients, industry, government, and academics to meet in-person to set the agenda for this study and interpret and communicate its findings. In addition to this, the PIs already contribute to other national advisory groups and industry meetings and will therefore use these in-person opportunities to be ambassadors for STRAVINSKY. For wider engagement on the project, we will engage with news media, including TV, radio, and print. As well as utilising local university press offices and networks, we have particularly strong links to the national health news media through the British Society for Immunology and our links to the Science Media Centre. We will use their extensive experience of communication in this area to ensure we reach out through different media to communicate our message and our findings with diverse groups.

Clinician engagement: The leadership team for this study come from multiple specialties and attend a wide range of academic conferences. As a result, there will be face to face presentation of key academic outputs from STRAVINSKY to national and international meetings. These would be attended by the individual for their CPD and so have not been specifically costed into this study. Academic meetings also provide the opportunity to meet with industry and patient organisations in-person and we will use these opportunities to arrange specialty specific meetings.

Version: 2.0 26.11.2023 IRAS:325967

Sponsor: University of Birmingham

21.0 Appendix 1 Treatment categories

The following medications will be considered as B-cell depleting treatment (group 17) for the purpose of this study.

B-CELL DEPLETING TREATMENT
Any monoclonal antibody against CD20, e.g.
Rituximab
Obinutuzumab
Ocrelizumab
Ofatumumab
Any bispecific antibody against CD20, e.g.
Mosunetuzumab
Epcoritamab
Glofitamab
Odronextamab
Chimeric antigen receptor (CAR-T) therapy directed against CD19, CD20, e.g.
Tisagenlecleucel
Axicabtagene Ciloleucel
Others
Alemtuzumab
ATG

The following medications will be considered as either chemotherapy, immunotherapy, or immunosuppressive medication for the purpose of this study (groups 18 & 20).

MEDICATIONS	CATEGORY OF MEDICATIONS
6-Mercaptopurine (6-MP)	Anti-metabolites
Abatacept	Biologic - Immune checkpoint
Abemaciclib	Biologic therapy - Other (Protein Kinase Inhibitor)
Acalabrutinib	B-cell targeted (BTK inhibitors)
Adalimumab	Biologic - Anti TNF

Afatinib	Biologic therapy - Other (Protein Kinase inhibitor)		
Apremilast	Biologic - Other (PDE4 Inhibitor)		
Aromatase inhibitors	Hormonal therapies		
Atezolizumab	Biologic therapy - Other (Checkpoint inhibitor)		
ATG	Biologic - polyclonal antibody against immune cells		
Azacitidine	Cytotoxic Chemotherapy		
Azathioprine	Anti-metabolites		
Baricitinib	JAK inhibitor		
Beclomethasone	Corticosteroids		
Betamethasone	Corticosteroids		
Bortezomib	Biologic therapy other		
Bosutinib	Biologic - Other (BCR-ABL inhibitor)		
Brentuximab	Biologic - Other (Anti CD30)		
Capecitabine	Cytotoxic chemotherapy		
Carboplatin	Cytotoxic chemotherapy		
Certolizumab	Biologic - Anti TNF		
Cisplatin	Cytotoxic chemotherapy		
Cortisone	Corticosteroids		
Crenolanib	Biologic - Other		
Cyclophosphamide	Cytotoxic chemotherapy		
Cyclosporine	Calcineurin inhibitor		
Cytarabine	Cytotoxic chemotherapy		
Daratumumab	B-cell targeted (anti-CD38)		
Dasatinib	Biologic - Other (BCR-ABL inhibitor)		
Daunorubicin	Cytotoxic chemotherapy		
Decitabine	Cytotoxic Chemotherapy		
Dexamethasone	Corticosteroids		
Docetaxel	Cytotoxic chemotherapy		
Doxorubicin	Cytotoxic chemotherapy		
Durvalumab	Biologic therapy - Other (Checkpoint inhibitor)		
Elotuzumab	B-cell targeted (other)		
Epirubicin	Cytotoxic chemotherapy		
Etanercept	Biologic - Anti TNF		
Etoposide	Cytotoxic chemotherapy		
Everolimus	Biologic therapy other		
Fludarabine	Cytotoxic chemotherapy		
Fluorouracil	Cytotoxic chemotherapy Cytotoxic chemotherapy		
Fulvestrant	Hormonal therapies		
Gefitinib	Biologic therapy - Other (Protein Kinase inhibitor)		
Gemcitabine	Cytotoxic chemotherapy		
Gemtuzumab ozogamicin	Biologic therapy other		
Gilteritinib			
Golimumab	Biologic - Other		
	Biologic - Anti TNF Riologic - Other (Apri II 22)		
Guselkumab	Biologic - Other (Anti IL23) Cortisporteroids		
Hydrocortisone	Corticosteroids Recall targeted (RTK inhibitors)		
Ibrutinib	B-cell targeted (BTK inhibitors) Cutatoxis shametherapy		
Idarubicin	Cytotoxic chemotherapy Richaria Other (DCR ARL inhibitor)		
Imatinib	Biologic - Other (BCR-ABL inhibitor)		
Infliximab	Biologic - Anti TNF		

Isatuximab	B-cell targeted (anti-CD38)
Ixekizumab	Biologic - Other (Anti IL17A)
Leflunomide	DMARDs - Other
Lenalidomide	Cytotoxic chemotherapy
Lestaurtinib	Biologic - Other
Melphalan	Cytotoxic chemotherapy
Methotrexate	DMARDs - Methotrexate
Methotrexate	DMARDs - Methotrexate
Methylprednisolone	Corticosteroids
Midostaurin	Biologic - Other
Mitoxantrone	Cytotoxic chemotherapy
Mycophenolate mofetil	Anti-metabolites
Nab-paclitaxel	Cytotoxic chemotherapy
Neratinib	Biologic therapy - Other (Protein Kinase inhibitor)
Nilotinib	Biologic - Other (BCR-ABL inhibitor)
Olaparib	Cytotoxic chemotherapy
Paclitaxel	Cytotoxic chemotherapy
Palbociclib	Biologic therapy - Other (Protein Kinase Inhibitor)
Pembrolizumab	Biologic therapy - Other (Checkpoint inhibitor)
Pertuzumab	Biologic therapy - Other (Protein Kinase Inhibitor)
Pomalidomide	Biologic therapy other
Ponatinib	Biologic - Other (BCR-ABL inhibitor)
Prednisolone	Corticosteroids
Quizartinib	Biologic - Other
Ribociclib	Biologic therapy - Other (Protein Kinase Inhibitor)
Ruxolitinib	Biologic - JAK inhibitor
Sarilumab	Biologic - Other (Anti IL6)
Secukinumab	Biologic - Other (Anti IL17A)
Sirolimus	Biologic therapy other
Sorafinib	Biologic - Other
Sulphasalazine	Non-myelosuppressive therapy
Tacrolimus	Calcineurin inhibitor
Tamoxifen	Hormonal therapies
Thalidomide	Biologic therapy other
Tocilizumab	Biologic - Other (Anti IL6)
Tofacitinib	JAK inhibitor
Toremifene	Hormonal therapies
Trastuzumab	Biologic therapy - Other (Protein Kinase Inhibitor)
Triamcinolone	Corticosteroids
Upadacitinib	JAK inhibitor
Ustekinumab	Biologic - Anti IL23
Vedolizumab	Biologic - α4β7 inhibitor
Vemurafenib	Biologic therapy - Other (Protein Kinase Inhibitor)
Venetoclax	B-cell targeted (BTK inhibitors)
Vinblastine	Cytotoxic chemotherapy
Vincristine	Cytotoxic chemotherapy

22.0 Appendix 2 Visit Summary

Timing	VISIT	Checklist	Responsibility (Local Study Team (L) or Central Study Team (C) or Participant (P)	
			Remote Cohort	In-person cohort
	PARTICIPANT IDENTIFICATION	Offer PIS	L	L
	SCREENING*	1) Informed Consent	P with L assistance if needed.	P with L assistance if needed.
		2) Check and confirm eligibility	P	P
		3) Trial registration onto REDCap	C/L	C/L
		4) Supply participants with Central Study Team contact details	C/L	C/L
As soon as possible after consent	VISIT 1	1) Complete online CRF	L	L
		2) Blood sampling	Р	L
		3) Nasal swab COVID-19 test kit	Provided by C, returned by P	by C, returned
		4) Antibody or swab result reported to patient		by P C
Remote cohort: Ideally 1 week before booster vaccine	VISIT 2	1) Complete online CRF	P with L assistance if needed.	L
In-person cohort: As above, but this visit can be omitted if it is less than 12 weeks after VISIT 1		2) Blood sampling	P	L
4-10 weeks post booster vaccine	VISIT 3	1) Complete online CRF	P with L assistance if needed.	L
		2) Blood sampling	Р	L
24-36 weeks post booster vaccine	VISIT 4	1) Complete online CRF	P with L assistance if needed.	L
		2) Blood sampling	Р	L
Anytime during study	ANYTIME	1. Participant to inform Central Study	P	P

	2.	Team if they have a COVID- 19 infection Return of		
	۷.	nasal swab to be repeated 2 weekly till negative	Provided by C, returned by P	Provided by C, returned by P

^{*}Individuals who self identifies for participation AND who are not registered with one of the participating sites will have their screening activities managed by the Central Study Team

23.0 Appendix 3 Statistical analysis plan

Sample size and randomisation

We have assumed that a sample size of 3000 is feasible and that this is likely to be distributed as 750 in the "low response/no response" group and 2250 in the "normal response" group. We might then wish to estimate what difference between these two groups we could detect with 90% power. We have good estimates from previous studies over time in vulnerable populations and have therefore considered a range of infection and hospitalisation rates that might be plausible for this group. We have also considered the statistically most conservative option by setting the proportion at 50%.

In all cases, we can detect an absolute difference between groups of less than 10% and often less than 5% even for the rarer outcome of hospitalisation. These are consistent with a standardised effect sizes ranging from 0.15 to 0.36 for infection, which are consistent with small to moderate effects. The effect size for hospitalisation is less certain and ranges from 0.24 consistent with a small effect through to 1.33, a very large effect.

We consider this reassuring as it indicates that for a wide range of scenarios, we should have adequate power in the whole cohort for our primary outcome of infection and we may have power to detect a moderate effect for the rarer secondary outcome of hospitalisation, depending on the prevailing population rates and the variant of interest.

We will monitor all the assumptions that underlie these calculations at least monthly and will discuss monthly at our Trial Meeting Groups, if there are any concerns about power for key analyses.

Randomisation procedure

This is an observational cohort and participants will not be randomised. The cohort may be used in future to recruit to randomised trials and the process for selection and randomisation would be described accordingly in the associated trial protocol.

Statistical analysis considerations

Definition of analysis populations

CV groups are defined below and are derived in part from the QCOVID4 risk groups.

The Healthy Control (HC) group represent a population sampled from the PITCH Study (Protective immunity from T-cells in healthcare workers).

Baseline characteristics

At baseline the following characteristics will be described for the study cohort:

- Demographics (Age, BMI, self-reported ethnicity, sex, Index of Multiple Deprivation)
- · Occupation, nature of work and type of personal protective equipment used during that work
- Medical conditions (self- reported)
- latrogenic immunosuppression (or within 6 months of iatrogenic immunosuppression including chemotherapy)
- · Vaccination history including COVID-19, influenza, and any test vaccines given
- · Known prior infection

Behavioural variables

If the participant self-isolated as a result of an illness in a household contact, we will collect data on the nature of that illness (when was illness, symptoms, severity, duration) and how many other household contacts were unwell.

Serological response

Time points for serological measurements: Assessment at 4 timepoints (Visit 1: baseline visit, Visit 2: before next vaccine dose, visit 3: 4 weeks post vaccine dose and Visit 4: 24-36 weeks post vaccine).

ii) 'Low' antibody range: Antibody values which lie within the lower 10th percentile of range of IgG antibody concentrations in HC following vaccine dose.

General analysis principles

- Summary statistics will include either mean, standard deviation, and/or median, interquartile range for continuous variables as appropriate to the distribution and n (%) for frequencies.
- The amount of missing data will be reported. Analysis will be of complete data and missing data will not be imputed.
- 5% two-sided level of statistical significance, with corresponding 95% confidence intervals presented where applicable.
- No adjustments for multiplicity are planned.

Planned analyses and reporting:

Primary Outcome

To assess the additive value of serological responses to CV status in predicting infection

The binary infection outcome will be captured by recording the timing and incidence rates of all infections from ≥14 days post vaccination given between Visit 2 until Visit 4 will be reported in the total combined CV groups, and by individual CV groups. We will describe the number and proportion of infections for each level of antibody response post-V3 (no, low, normal)

The primary analysis will be undertaken using a logistic regression model with infection as the outcome and antibody response post-V3 as a binary variable as the exposure. We will present odds ratios with 95% confidence intervals for the unadjusted model, as well as for a model adjusted for the baseline and behavioural variables as well as any COVID-19 therapy received in the community, preadmission and in hospital (where data available).

Assuming serology is predictive of outcome, we will build a model to explore the predictive value of key patient data and the added value of serological results. We will explore the discrimination and calibration of a model only including baseline and behavioural variables compared to this model also including serological response. Discrimination will be determined by Harrell's C statistic and calibration will be determined by the predicted probabilities for infection. It is not possible to externally validate this model in this study; instead 1000 bootstrapped samples will be used in determining the 95% confidence intervals for the C statistic.

As a sensitivity analysis we will also consider serological response as a continuous variable. We will also consider time to first infection as a time to event outcome with death as a competing risk. This will be implemented in Stata using the *stcrreg* command. The same covariates will be included in the adjusted model as for the primary analysis. Unadjusted and adjusted analyses will present hazard ratios with 95% confidence intervals.

To assess the additive value of serological responses to CV status in predicting severe outcome We will undertake an analysis using the same modelling approach as for the primary outcome but with a composite outcome of severe infection (infection, hospitalisation or death).

Secondary Outcomes

To evaluate the serological vaccine responses of CV patients to new vaccines

28-day post vaccine (Visit 3) IgG antibody levels (BAU/ml) will be reported in HC and CV individuals. The proportion of combined and individual CV groups with no, low or normal Visit 3 antibody levels will be reported.

The median (IQR) of Visit 3 antibody levels in each CV group will be reported, alongside the values for HC.

Logistic regression models will be used to assess factors that contribute to serological response as a binary outcome with normal compared to lack of response (no/low). The model will include the baseline variables set out in **Section 5.2** and further variables may be added to the model if evidence emerges that such variable impacts on vaccine responses to vaccines. Univariable logistic regression will be used to explore the unadjusted relationship of each variable with the outcome and multivariable logistic regression will be used to explore the independent relationship of each variable with the outcome. We will report odds ratios and 95% confidence intervals for all models.

To assess serological responses, antibody boosting, antibody waning and correlation with infection

The above analyses focus primarily on Visit 3 (4 weeks post vaccine booster). Similar analysis will be performed from antibody status at time point Visit 1, with adjustment required for time post-vaccine to Visit 1, and also vaccine type pre-Visit 1 (Wuhan or bivalent vaccine). Infection outcomes will be described up until Visit 2. Assessment of waning (rate of antibody concentration decline) will also be described between Visit 1 and Visit 2. Assessing differences between HC versus CV group, but also individual groups. Similar waning analysis will be reported between Visit 3 and Visit 4.

Descriptive changes in antibody levels between Visit 3 and Visit 4 by CV groups will also be reported.

Sponsor: University of Birmingham

Antibody binding to VOC

This analysis will be focused on samples derived from Visit 1 and at subsequent follow up points, assuming this will capture most diversity in VOC during the study duration. Antibody binding to SARS-CoV-2 WT will be compared against binding to the dominant VOCs in participants with detectable antibodies and reported as fold-change (e.g. VOC/WT) and absolute change.

Subgroup analyses

We will present the number and proportion of patients with adequate and inadequate antibody response in each disease subgroup. We will also present the number and proportion in each of these groups with COVID-19 infection and COVID-19 related hospitalisation. Provided there are sufficient numbers in each group, we will undertake exploratory analyses using the same approach as for the analysis of the primary outcome in the full cohort.

Exploratory Analyses

Evaluation of QCOVID4 risk score

i) Is the QCOVID4 score associated severe COVID-19 in our cohort? (low/med/high and quantitative analysis)

For all participants, we will calculate the QCOVID risk score and explore whether this is associated with adverse outcome in this cohort. QCOVID was derived for hospitalisation and death as an outcome so we will explore this relationship in the first instance. However, we will also test whether QCOVID is valid for predicting our primary outcome of infection. The key outcomes in our cohort are binary so logistic regression will be used, with QCOVID risk score as the exposure variable. In line with the common protocol published for validation of the QCOVID algorithm (Kerr et al BMJ Open 2022) (but using the latest QCOVID4 score), Harrell's C statistic will be used to determine model discrimination and predicted probabilities of outcomes will be used to determine model calibration.

ii) Is the QCOVID4 score associated with anti-S titres in our cohort? (low/med/high and quantitative analysis)

We will quantify the relationship between QCOVID4 risk score and the anti-S titres using Pearson or Spearman's correlation, as appropriate to the distribution. We will also summarise the mean QCOVID score for each group of antibody results (none, low, normal) and use ANOVA to test for between group differences.

iii) Is the QCOVID4 score associated with T-cell responses in our cohort? (positive/negative and quantitative)

We will undertake the same analyses described in ii above for T-cell responses in relation to QCOVID4 risk score.

iv) Does the addition of serology measurements enhance QCOVID4 score?

Version: 2.0 26.11.2023 IRAS:325967

If QCOVID4 score shows good model discrimination and calibration with respect to adverse outcome or infection in our cohort, we will explore whether serology measurements improve the model. Serology measurements will be added to the logistic regression model and model fit diagnostics produced as per the common protocol (see i above). We will test these nested models to determine whether serology measurements significantly improve the model.

B) Identify additional laboratory methods to predict COVID-19 infection/hospitalisation if antibody testing fails to predict relevant clinical outcomes

Peripheral blood (and mucosal) samples will be stored, so that alternative assays can be performed to look for correlates of protection should blood anti-S IgG fail to stratify for COVID-19 risk. These will include:

- i) Antigen-specific T-cell response e.g. through IFNy ELISpot (Oxford, Southampton)
- ii) Functional antibody assays e.g. live virus neutralisation and others (Oxford, Southampton)
- iii) Mucosal secretion serology on the MSD platform to monitor mucosal immunity (Birmingham) \square IgG and IgA quantification on samples from Visit 2 and Visit 3. Logistic regression analysis will be used to study the association between mucosal antibody titres and serum/plasma antibody titres, infection episodes and hospitalisation.

Descriptive analysis of these assays will be performed, statistical assessment will include, but will not be limited, to the following analyses:

C) To evaluate cellular responses to new vaccines in CV patients

28-day post vaccine (Visit 3) T-cell responses will be reported in HC and 400 CV individuals, as a binary value of present or absent.

The proportion of combined total and individual CV groups with present or absent T-cell responses will be reported.

The median (IQR) of T-cell responses (per 10⁶ PBMCs) will be reported in HC and 400 CV individuals. Multiple regression models will be fit to assess response, the following variables have been highlighted for inclusion in the model, using in the variables described in the serological models.

Pearson's Correlation or Spearman's Rank, as appropriate to the distribution. will be used to quantify the correlation between serological and cellular responses, in individual CV groups and combined group.

D) To evaluate cellular responses to new VOCs in CV patients

IFN ☐ reactivity in T-cells to variant spike peptides and compare this against reactivity to WT spike and expressed as fold change and absolute values for 2 time points 12 months apart.

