5.0 Study population and eligibility criteria

5.1 Patient selection

Participants in this study will have an underlying disorder which has identified them as being clinically vulnerable. The disease and treatment groups eligible for participation (**TABLE 2, page 13**) in STRAVINSKY may alter throughout the study depending on the results from the retrospective analysis or other new knowledge/discussions such as the report from the Independent Advisory Group for COVID-19 medicines.⁵

TABLE 2. Groups eligible for participation

Group	Disease related groups (n=120-140 per group)				
1	Chronic lymphoproliferative disorders (footnote 1)				
2	Plasma cell disorders (footnote 2)				
3	Myelodysplastic syndrome (MDS) or (myeloproliferative neoplasms MPN) (footnote 3)				
4	Sickle cell disease, thalassaemia, or rare inherited anaemias				
5	Active malignancy diagnosed within 2 years of study consent (excluding non-melanoma skin cancer, non-invasive bladder cancer and localized squamous cell carcinoma of cervix)				
	(Note: participants who have received radiotherapy or systemic anti-cancer treatment within the last 26 weeks should be included in groups 18 and 19 first).				
6	Down's syndrome and learning disability				
7	Neurological diseases (Parkinson's and mult	iple sclerosis) (footnote 4)			
8	HIV				
9	Common variable immunodeficiency an prophylactic antibiotics and/or immunoglob	d secondary immunodeficiency (requiring ulin)			
10	Cirrhosis (footnote 5)				
11	Chronic respiratory conditions (footnote 6)				
12	Chronic kidney disease (CKD) stage 4-5 (foot	note 7)			
13	Diabetes mellitus (Type 1 and 2)				
14	Cardiac failure				
	Treatment-related group	Timing			
	(n=120-140 per group)				
15	Previous recipients of a solid organ transplant (SOT)	At any time			
16	Recipient of a haematopoietic stem cell transplant (HSCT)	Within 52 weeks at time of study consent			
17	Recipient of B-cell depleting treatment (APPENDIX 1 for details)	Within 52 weeks at time of study consent			
18	Recipient of systemic anti-cancer therapy e.g. chemotherapy or immunotherapy and others (APPENDIX 1 for details)	Ongoing or within last 26 weeks at time of study consent			
19	Recipient of radiotherapy	Ongoing or within last 26 weeks at time of study consent			
20	Autoimmune disease on systemic immunosuppressive* medication (APPENDIX 1 for details)	Ongoing or within last 26 weeks at time of study consent			

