6.0 Prospective study

6.1 Study design and overview

This is a multicentre prospective, observational cohort study (**FIGURE 1**). Patients will provide samples and clinical data on 4 different occasions over 12-18 months. For each of the 4 visits individuals will be allocated to be involved in the study either remotely or attend in-person.

3000 individuals will be recruited in total; for 2600 of these patients (remote cohort), their commitment to the study will be entirely remote.

400 individuals (in-person cohort) will be invited to attend a sampling appointment at one of the 4 inperson sampling sites (Birmingham, Southampton, Imperial or Oxford), for each of the 4 study visits. The aim will be to recruit between 120 and 140 individuals per disease/treatment group as detailed in **TABLE 2.**

13 | Page STRAVINSKY Protocol

^{*} This enables assessment of the primary outcome and response to bivalent vaccine. It is highly likely that policy on these licensed treatments will change, in which case we may submit an amendment to individuals receiving SARS-CoV-2 monoclonal Abs.

Informed consent and data collection will predominantly be collected online via a REDCap database. Patients and sites without access to devices or internet will be consented via telephone, the signed paper consent form will then be sent to the participant to counter sign, and they will be asked to post this back to the central study team.

Participants without access to devices to internet will also be offered face to face appointments where the patient can either be supported by the research nurse to complete the online consent form or the participant can sign a paper consent form. If paper consent forms are used, they will be transcribed/scanned into REDCap and the original paper source document will be stored at the recruiting site for the duration of the study. Any case report form (CRF) data collected face to face or via telephone will also be transcribed directly into the database by each local clinical care team. Paper CRF data and consent forms will be transcribed/scanned into REDCap. The original paper documents will be stored at the recruiting site.

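### The 6-month look-back for iatrogenic immunosuppression leaves out HSCT and B-cell-depleting treatment given 26 to 52 weeks before consent, and no other listed covariate captures it

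*Protocol*

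**What the plan says.** Protocol Appendix 3, Baseline characteristics, lists iatrogenic immunosuppression with the extension "or within 6 months of iatrogenic immunosuppression including chemotherapy". The other listed items are demographics, occupation and protective equipment, self-reported medical conditions, vaccination history and known prior infection. Neither Table 2 group nor time since HSCT or B-cell depletion is on the list.

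The list is introduced as descriptive, but it also supplies covariates:

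- **Primary outcome.** The adjusted logistic model is "a model adjusted for the baseline and behavioural variables", plus COVID-19 therapy received. The competing-risk sensitivity analysis uses the same covariates.
- **Prediction model.** Baseline and behavioural variables form the base model against which the added value of serology is judged.
- **Secondary outcome.** "Logistic regression models will be used to assess factors that contribute to serological response as a binary outcome". This model takes the baseline variables from a Section 5.2. In this document Section 5.2 holds the inclusion criteria, so the Appendix 3 list is presumably meant.

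Section 5.1, Table 2, gives two windows for the time-limited treatment groups. Groups 16 (HSCT) and 17 (B-cell-depleting treatment) qualify "Within 52 weeks at time of study consent". Groups 18 to 20 qualify "Ongoing or within last 26 weeks at time of study consent".

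**The concern.** Six months matches the 26-week window of groups 18 to 20 but covers only half of the 52-week window of groups 16 and 17. Take someone whose only relevant treatment was an anti-CD20 antibody nine months before consent. That person is enrolled because of the treatment, yet a coder applying the only time rule in Appendix 3 can record no iatrogenic immunosuppression.

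These groups can be expected to include many poor vaccine responders. Placing some of them in the reference category has two consequences:

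1. Adjustment for immunosuppression is incomplete, so part of its effect on infection can remain in the antibody odds ratio.
2. The base prediction model is weaker than it need be, so serology can appear to add more than it does.

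If the serological-response model uses the same list, its coefficient for immunosuppression is also pulled towards 1.

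**Working it through.** **Windows.** Six months is 365.25/2 = 182.6 days and 52 weeks is 364 days. The part of the group 16 and 17 window outside the look-back is 364 − 182.6 = 181.4 days, and 181.4/364 = 49.8%, about half.

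**People.** Section 6.1 states: "The aim will be to recruit between 120 and 140 individuals per disease/treatment group". Two groups give 240 to 280 people, or 8.0 to 9.3% of 3000. The share treated 26 to 52 weeks before consent is not in the documents, so a range is assumed:

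| Assumed share | People | % of 3000 |
|---|---|---|
| 25% | 60–70 | 2.0–2.3 |
| 50% (even timing) | 120–140 | 4.0–4.7 |
| 75% | 180–210 | 6.0–7.0 |

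Each row is an upper bound on those coded no, because anyone currently on another immunosuppressant is coded yes.

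**Primary model, illustration.** All rates here are assumptions. Take 130 per group over 20 groups, giving 1820 untreated and 780 treated (six treatment groups). No/low response is 15% in the untreated, 50% in treated people coded yes and 70% in the miscoded. Infection risk in the untreated is 20%, the true antibody odds ratio (OR) is 1.0, and immunosuppression multiplies infection odds by 2, so treated risk is 0.5/1.5 = 33.3%. With 130 miscoded, the coded-no stratum is:

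- no/low response: 1820 × 0.15 = 273 untreated and 130 × 0.70 = 91 miscoded; infected (54.6 + 30.3)/364 = 23.3%
- normal response: 1547 untreated and 39 miscoded; infected (309.4 + 13.0)/1586 = 20.3%
- stratum OR = (0.2333/0.7667)/(0.2033/0.7967) = 1.19

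The coded-yes stratum has OR 1.0. A logistic model fitted to the expected counts of both strata gives 1.11. Varying the inputs:

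| Infection odds multiplier | 130 miscoded | 65 miscoded |
|---|---|---|
| 1.5 | 1.06 | 1.03 |
| 2 | 1.11 | 1.06 |
| 3 | 1.18 | 1.09 |

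For scale, the unadjusted OR with multiplier 2 and 130 miscoded is (193.3/495.7)/(430.7/1480.3) = 1.34. The imperfect covariate still removes most of the confounding.

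**Serological-response model, illustration (same assumed response rates).**

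- Coded by the 6-month rule: reference risk = (273 + 91)/1950 = 0.187; OR of 0.50 against 0.187 = 4.4.
- Coded by treatment actually received: exposed risk = (650 × 0.50 + 91)/780 = 0.533; OR of 0.533 against 0.15 = 6.5.
- With 50% non-response in the miscoded, the OR falls from 5.7 to 4.8; with 90%, from 7.4 to 4.0.

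**The case against.** A reader might infer four stronger things that the documents do not support.

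- **That the covariate contradicts the protocol's own definition of immunosuppression.** Table 2 is a list of groups eligible to take part and defines no such variable. It includes radiotherapy recipients, and the Appendix 1 drug list for groups 18 and 20 includes tamoxifen and aromatase inhibitors. The fault is a gap in a covariate, not a clash of two definitions.
- **That everyone treated nine months ago is coded no.** The item also covers current immunosuppression, and its 6 months is not expressly counted from the last dose. A coder could count persisting B-cell depletion as current. The text neither says so nor rules it out, so two coders could differ on the same person.
- **That half of groups 16 and 17 are miscoded.** That is a ceiling under even timing. Allocation follows the first applicable row from 15 to 20, so groups 16 and 17 also take in people with ongoing group 18 or 20 treatment, and ongoing immunosuppressive treatment is coded yes.
- **That the fall from 6.5 to 4.4 is the size of the problem.** It is a crude odds ratio for one covariate in a secondary model, on assumed rates, and it stays at 4 or above throughout.

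It can also be said that the plan handles part of this elsewhere. The primary heading speaks of value added to CV status, results are reported by CV group, within-group models are planned if numbers allow, and variables may be added to the serological-response model. If Table 2 group did enter the adjusted model, most of the problem would disappear. No model statement names it, however, and self-reported conditions do not record a treatment. The gap in the adjusted primary and base prediction models stands.

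**Conclusion.** The point holds as a gap in a stated covariate rule. Treatment 26 to 52 weeks before consent can be the sole reason for enrolment in group 16 or 17, yet it falls outside the look-back and no other listed covariate picks it up. The number affected is unknown: at most about 120 to 140 people (4 to 5% of 3000) if treatment dates are evenly spread, and fewer with concurrent agents.

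The bias in the adjusted antibody odds ratio is probably modest, 1.03 to 1.18 around a true 1.0 in the illustration. Its true size cannot be computed from the documents. Its direction rests on the assumption that treated people have higher infection odds; if they avoid exposure and are infected less often, it reverses. The effect on the serological-response model depends on its Section 5.2 pointer meaning the Appendix 3 list. The unadjusted primary odds ratio and the by-group descriptions are unaffected. The point is worth correcting because the change is cheap, not because it threatens the main result.

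**What to change.** In Appendix 3, keep the existing 6-month item for other treatments and add a separate covariate level for HSCT or B-cell-depleting treatment within 52 weeks of consent. Derive it from the treatment dates used for eligibility and from the medication history that section 6.5.1 takes from hospital and GP records. State that this level applies whether or not another agent is being taken, so that all coders classify alike. Correct the Section 5.2 pointer in the serological-response model at the same time.

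Do not code all group 18 to 20 treatment as immunosuppression. Those groups include people given radiotherapy alone or hormonal therapy alone, and counting them would introduce a new misclassification.

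The cost is a short edit, a recode of dates already needed for eligibility, and one extra model level. Eligibility and clinical management do not change.
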